### **7.3.3 Secondary analyses**

In addition to the primary analysis, a secondary analysis of Girerd questionnaire scores will be performed.

This questionnaire is composed of 6 binary questions (yes/no) and is used to assess treatment compliance. The final score obtained is the number of questions to which the patient responded 'yes'. Thus, the score ranges from 0 to 6.

A patient will be classified as:

- Good compliant: score = 0.
- Minor non-compliant: score = 1 or 2.
- Non-compliant: score > 2.

A sub-group descriptive analysis of patients per score category on D30, D60 and D90 will be presented: number of observed values, percentage, and 2-sided 95% confidence interval.

In addition, the percentage of patients with good compliance (score = 0) to the percentage of patients with minor non-compliance and / or non-compliance (score > 0) will be compared at each time point (D30, D60, D90), between the 2 groups of patients ('With nurse-led follow-up' and 'Without nurse-led follow-up'), using Chi-2 or Fisher-exact test.

The cumulated doses (mg) of the oral targeted therapy not taken during the 3-month follow-up by decision of the medical team (with details by type: dose reduction, temporary or definitive discontinuation) / by decision of the patient him/herself (with details by type: dose reduction, temporary or definitive discontinuation) will be described for each follow-up group, using number of observed values, mean, standard deviation, median, lower quartile, upper quartile, minimum, maximum, 2-sided 95% confidence interval of the mean.

Analysis of other secondary endpoints will simply be descriptive and inferential as described in the general statistical considerations, namely:

- Quantitative variables:
  - VAS score (0–10) for overall patient satisfaction with the level of self-care (information, counselling, advice...) at D90.
  - Absolute variation observed for the quality of life questionnaire FACT Lung score between D30 and D0, between D90 and D0, and between D30 and D90.
  - Duration of unplanned hospitalisations during the 3-month follow-up.
  - VAS score (0–10) for overall investigator satisfaction with the level of patient self-care at D90.
  - VAS score (0–10) for overall general practitioner satisfaction with the level of patient self-care at D90 (only for the patients with 'remote additional personalised nurse-led follow-up').

- VAS score (0–10) for overall pharmacist satisfaction with the level of patient self-care at D90 (only for the patients with 'remote additional personalised nurse-led follow-up').
- Qualitative variables:
  - Number of emergency admissions during the 3-month follow-up.
  - Number of unplanned hospitalisations during the 3-month follow-up.
  - Number of unplanned visits to the investigator during the 3-month follow-up.
  - Number of unplanned visits to a specialist, whatever is his specialty, other than the investigator during the 3-month follow-up.
  - Number of unplanned visits to the general practitioner during the 3-month follow-up.
  - Number of calls made by the patients to their general practitioner during the 3-month follow-up.
  - Number of calls made by the general practitioner to their patient during the 3-month follow-up.
  - Number of calls made by the patients to their medical team during the 3-month follow-up.
  - Number of calls made by the medical team to their patient during the 3-month follow-up.
  - Number of calls between the general practitioners and the medical team during the 3-month follow-up.

Moreover, the impact of patient follow-up on the evolution of parameters measured repeatedly during the study will be studied using mixed model repeated measures, in which the patient will represent a random effect and the follow-up group will represent a fixed effect. A Follow-up\*Visit interaction will demonstrate the existence of a different evolution of the parameters according to the type of follow-up. This analysis will only be performed for the criteria measured several times during the follow-up.

The identification of possible predictors of non-compliance will be conducted using a generalized mixed effect model (proc GLIMMIX in SAS) by including the patients and investigators characteristics and the group (with/without additional nurse-led follow-up) as explanatory variables (these characteristics will be detailed with more precision in the Statistical Analysis Plan [SAP]). A non-compliant patient will be defined as a patient with the ratio between the cumulated dose actually taken during the first 3 months of treatment and the cumulated dose taken during the first 3 months of treatment without interruption and dose reduction is strictly less than 80%. This modelling will be exploratory.

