## **2. RATIONALE AND OBJECTIVES**

### **2.1 RATIONALE FOR PERFORMING THE STUDY**

The current management of patients with stage IIIb/IV NSCLC uses targeted therapy (ESMO 2012) as first, second and third-line therapy. Targeted therapies are generally oral treatments which makes the patient responsible of the treatment intake. This approach affects patient compliance to treatment and management of AEs. In routine clinical practice, patients are regularly seen by their oncologists and a support program can be established following the recommendations of the Cancer Plan 3 (developing in the certification of healthcare institutions an approach to help patients with their care, improve communication and coordination between general practice and hospital, try new modalities of organisation in the management of patients treated with oral targeted therapy involving health professional in general practice and in hospital). A regular nurse-led telephone follow-up at the beginning of treatment may improve patient compliance. Therefore, the impact of the implementation of such a follow-up program on patient compliance to therapy will be evaluated in this real-life study.

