## **5.2 SECONDARY ENDPOINTS**

### **5.2.1 Secondary endpoints**

The following secondary endpoints will be evaluated in the study:

- Score (0–6) obtained with the Girerd questionnaire at D30, D60 and D90.
- Cumulated dose of oral targeted therapy not taken (all categories) following decision of the medical team.
- Cumulated dose of oral targeted therapy not taken due to dose reduction following decision of the medical team.

- Cumulated dose of oral targeted therapy not taken due to temporary or definitive interruption following the medical team decision.
- Cumulated dose of oral targeted therapy not taken (all categories) following patient decision.
- Cumulated dose of oral targeted therapy not taken due to dose reduction following patient decision.
- Cumulated dose of oral targeted therapy not taken due to temporary or definitive interruption following patient decision.
- VAS score (0–10) for overall patient satisfaction with the level of care (information, advice) at D90.
- Absolute variation observed for the quality of life questionnaire FACT Lung score between D30 and D0, between D90 and D30 and between D90 and D0.
- Number of emergency admissions (related to the treatment) during the 3-month follow-up.
- Number and duration of unplanned hospitalizations (related to the treatment) during the 3-month follow-up.
- Number of unplanned visits to the investigator during the 3-month follow-up.
- Number of unplanned visits to a specialist, whatever is his specialty, other than the investigator during the 3-month follow-up.
- Number of unplanned visits to the general practitioner during the 3-month follow-up.
- VAS score (0–10) for overall investigator satisfaction with the level of patient care at D90.
- VAS score (0–10) for overall general practitioner satisfaction with the level of patient care at D90 (only for the patients with 'remote additional personalised nurse-led follow-up')
- VAS score (0–10) for overall pharmacist satisfaction with the level of patient care at D90 (only for the patients with 'remote additional personalised nurse-led follow-up').
- Number of calls made by the patients to their general practitioner during the 3-month follow-up.
- Number of calls made by the general practitioner to the patient during the 3-month follow-up.
- Number of calls made by the patients to their medical team during the 3-month follow-up.
- Number of calls made by the medical team to their patient during the 3-month follow-up.

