### **5.2.2      Assessment methods**

Girerd questionnaire is a questionnaire composed of 6 binary questions (yes/no) and is used to assess treatment compliance. The final score obtained is the number of questions to which the patient responded 'yes'. Thus, the score ranges from 0 to 6.

FACT Lung quality of life questionnaire is composed of 27 items of the FACT-G questionnaire, with the following 4 dimensions: physical well-being, social well-being,

emotional well-being, and functional well-being. It is composed of 9 questions specific to lung cancer. Each of the 36 questions is scored from 0 to 4 (cf. Section 7.3.3 for more details on the analysis of these questionnaires).

Cumulated dose (mg) of oral targeted therapy not taken between 2 visits is the sum of the doses (mg) of the tablets not taken by the patient. The cumulated dose (mg) of the oral targeted therapy not taken during the 3-month follow-up is the sum of the doses (mg) cumulated not taken between 2 visits during the 3-month follow-up. This dose can be calculated overall and by reason for not taking the prescribed dose: dose reduction, temporary or definitive discontinuation following decision of the medical team / patient decision.

VAS scores will be presented in the form of a horizontal ungraduated line of 10 cm, with the following extremities: left, 'completely unsatisfied' and right, 'very satisfied'. The number of points (0 to 10) obtained in VAS corresponds to the distance (cm) between the left extremity of the line and the mark placed on the line by the patient, investigator, general practitioner, or pharmacist to assess patient's level of satisfaction.

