## **7.6 DETERMINATION OF SAMPLE SIZE**

In the absence of dose discontinuation or reduction, the cumulated dose of oral targeted therapy should be 3600 mg of afatinib, which corresponds to a daily dose of 40 mg for 90 days.

Clinical trials performed with afatinib before its marketing authorisation showed that over the first 3-month follow-up the mean dose of 3000 mg was taken (which corresponds to a dose intensity of 83%) (Boehringer Ingelheim First Interim Study Report 1200.32).

It was estimated that the mean dose observed in the group ‘without remote additional personalised nurse-led follow-up’ will be similar to the mean dose observed in the afatinib clinical trials and that adding an additional nurse-led follow-up will increase the mean dose by 6% (3180 mg, dose intensity of 88%).

As such, the number of patients to be included in the study has been calculated on the basis of a t-test for 2 unmatched samples with the following hypotheses:

- Mean cumulated dose of oral targeted therapy taken during the 3-month follow-up in the group ‘without remote additional personalised nurse-led follow-up’: 3000 mg (dose intensity of 83%).
- Mean cumulated dose of oral targeted therapy taken during the 3-month study in the group ‘with remote additional personalised nurse-led follow-up’: 3180 mg (dose intensity of 88%).
- Standard deviation of the cumulated dose of oral targeted therapy taken during the 3-month follow-up in both groups: 500.
- Type I error:  $\alpha = 0.05$ .
- Type II error:  $\beta = 0.20$  (power = 80%).
- Ratio ‘with remote additional personalised nurse-led follow-up’ group/‘without remote additional personalised nurse-led follow-up’ group = 3.

Using these hypotheses, in order to show an increase in the cumulated dose with the addition of 3-month nurse-led follow-up, it is necessary to have 82 patients in the group ‘without remote additional personalised nurse-led follow-up’ and 246 patients in the group ‘with remote additional personalised nurse-led follow-up’.

If it is considered that 20% of included patients will be non-evaluable for the primary criterion, it is necessary to include 99 patients in the group ‘without remote additional personalised nurse-led follow-up’ and 297 patients in the group ‘with remote additional personalised nurse-led follow-up’, i.e. 396 patients in total which can be rounded up to 400.

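### The exploratory 'non-compliant patient' outcome in Section 7.3.3 is really dose intensity below 80%, so it merges team-ordered with patient-decided shortfall and can label a fully adherent patient non-compliant

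*Combined protocol and SAP*

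**What the plan says.** The last paragraph of Section 7.3.3 plans a generalised mixed model to look for predictors of non-compliance, "by including the patients and investigators characteristics and the group (with/without additional nurse-led follow-up) as explanatory variables". The binary outcome is defined there: the numerator is the dose actually taken over the first three months, and the patient is non-compliant if its ratio to "the cumulated dose taken during the first 3 months of treatment without interruption and dose reduction is strictly less than 80" per cent. The paragraph adds: "This modelling will be exploratory". It leaves the detail of the covariates to the SAP, but not the outcome definition.

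Section 7.6 gives the full dose. Without any discontinuation or reduction, the total "should be 3600 mg of afatinib, which corresponds to a daily dose of 40 mg for 90 days". It calls the ratio of mean dose to that total the dose intensity.

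Elsewhere the protocol separates shortfall by who decided it. Section 5.2.1 lists matched endpoints for the medical team and for the patient, for example "Cumulated dose of oral targeted therapy not taken due to temporary or definitive interruption following the medical team decision". Section 5.2.2 says the dose not taken can be calculated by reason: "dose reduction, temporary or definitive discontinuation following decision of the medical team / patient decision". Section 7.3.3 describes both by group.

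**The concern.** The model's stated target is non-compliance, but the denominator of its outcome is the maximum uninterrupted dose, not the dose ordered. A shortfall created by the medical team counts exactly as one created by the patient. None of the covariates named in Section 7.3.3 records who decided.

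Patient characteristics that go with toxicity or early treatment failure could then be reported as predictors of poor compliance. The group coefficient would combine two effects: any change in patient behaviour, and any change in the team's decisions to reduce or stop. At stake is the interpretation of one exploratory model.

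**Working it through.** **Inputs.** Full dose 3600 mg, control mean 3000 mg, nurse-group mean 3180 mg, SD 500 mg (Section 7.6). Tablet strengths 20, 30, 40 and 50 mg (Section 5.1.2). Threshold 80%, strict (Section 7.3.3). Assumption: the denominator in Section 7.3.3 is the 3600 mg of Section 7.6, since 7.3.3 gives no figure.

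**The plan's own figures.** 40 × 90 = 3600 mg; 3000/3600 = 83.3%; 3180/3600 = 88.3%. These agree with the stated 83% and 88%.

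**Cut-off.** 0.80 × 3600 = 2880 mg.

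**Patients who start at 40 mg and take every ordered tablet:**

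| Team-ordered change | mg taken | Ratio to 3600 | Label |
|---|---|---|---|
| 30 mg after 14 days | 14×40 + 76×30 = 2840 | 78.9% | non-compliant |
| 30 mg after 18 days | 18×40 + 72×30 = 2880 | 80.0% | not labelled |
| 30 mg after 28 days | 28×40 + 62×30 = 2980 | 82.8% | not labelled |
| 20 mg after 45 days | 45×40 + 45×20 = 2700 | 75.0% | non-compliant |
| Stop at day 60 | 60×40 = 2400 | 66.7% | non-compliant |
| Interruptions totalling 18 days | 72×40 = 2880 | 80.0% | not labelled |
| Interruptions totalling 19 days | 71×40 = 2840 | 78.9% | non-compliant |

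The label therefore applies to a reduction to 30 mg after fewer than 18 days at 40 mg, to 20 mg after fewer than 54 days, or to a stop before day 72.

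**The opposite error.** If the denominator stays at 3600 mg for a patient moved to 50 mg after 30 days, the ordered dose is 30×40 + 60×50 = 4200 mg. That patient could miss 4200 − 2880 = 1320 mg (31% of what was ordered) and not be labelled.

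**How many patients could carry the label.** Assuming a normal distribution with the plan's means and SD:

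- Controls: P(Z < (2880 − 3000)/500) = P(Z < −0.24) = 40.5%.
- Nurse group: P(Z < (2880 − 3180)/500) = P(Z < −0.60) = 27.4%.

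The documents do not give the part due to team decisions. If it were 25%, 50% or 75%, about 10%, 20% or 30% of controls (0.405 × share) and 7%, 14% or 21% of the nurse group (0.274 × share) would carry the label because of team orders.

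The normal shape is rough. It puts P(Z > 1.20) = 11.5% of controls and P(Z > 0.84) = 20.0% of the nurse group above 3600 mg, which would require 50 mg tablets.

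**The case against.** The best defence is the protocol's own vocabulary. The synopsis and Section 2.2.2 speak of non-compliance following a decision of the medical team, and Sections 2.2.1 and 7.3.2 express overall compliance as cumulated dose from any cause. The 80% rule dichotomises that same quantity, so it is consistent with the primary endpoint. This stands, and it makes the matter partly one of naming. It does not remove the mixing: Section 2.2.2 uses the broad term in two separate objectives, one per decision-maker, and in Section 6.2.3 the nurse asks whether the medicine was taken as the doctor prescribed.

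Second, patient behaviour is covered elsewhere: dose not taken by patient decision is an endpoint, and the Girerd categories are compared by group at D30, D60 and D90. This stands too, but neither is a predictor model.

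Third, a reader might infer that the group effect in this model reflects medical decisions and not patient behaviour. The documents do not support that; the outcome mixes both. The introduction expects the calls to help manage toxicity, and Section 3.1 sends call reports to the investigator the same day, so team decisions may lie on the intended pathway. For the same reason, an outcome based on prescribed dose does not give a plainly cleaner group comparison.

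Fourth, deaths and early stops count only for patients who are in the model. Section 7.3 restricts the analysis population to patients with primary-criterion data. That limit is accepted.

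**Conclusion.** The point holds at minor severity. The outcome is relative dose intensity below 80% under the name of non-compliance, and patients who follow orders exactly can be labelled non-compliant. The arithmetic rests only on the 3600 mg denominator and the tablet strengths.

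Three stronger readings are not supported:

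- A reader might infer that any team-ordered reduction or stop produces the label. Only changes that bring the total below 2880 mg do.
- A reader might take 40.5% and 27.4% as misclassification rates. They are the expected shares below the cut-off from any cause, under an assumed normal shape, and the team-decided part is unknown.
- A reader might conclude that the trial's main compliance result is compromised. The model is declared exploratory, and the primary test, the sample size and the listed secondary endpoints do not use this definition.

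What remains is that predictors found by this model may be predictors of toxicity or prescriber decisions, and the model cannot tell these from predictors of patient non-compliance.

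**What to change.** In Section 7.3.3 and the SAP:

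1. Rename the present outcome 'dose intensity below 80%' and keep its model.
2. Fit the same exploratory model to a second outcome: mg taken / (mg taken + mg not taken for reasons other than a medical-team decision), below 80%.
3. State how days after death, and shortfall with no recorded reason, enter this second ratio.

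Under the second outcome, the adherent patients in the table above score 100%: for example 2840/(2840 + 0) and 2400/(2400 + 0). A patient stopped by the team at day 50 (2000 mg ordered) who missed twelve 40 mg tablets (480 mg) scores 1520/2000 = 76% and is labelled. Dividing the patient-decided shortfall by 3600 mg instead is not equivalent: 480/3600 is only 13.3%.

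The tablet counts (Section 5.1.2) and the attribution by decision-maker (Section 5.2.2) are already planned, so no new CRF fields are needed and no clinical rule changes. The cost is a few sentences and one further model. The downsides are fewer events and so less precision, unstable ratios for patients with very short exposure, and a group effect that needs cautious reading because prescribed dose is itself post-randomisation.

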### 7.3.4 Safety analyses

Safety analyses will be performed on all patients who received at least one dose of oral targeted therapy during the 3-month follow-up. Only events considered related to oral targeted therapy will be considered in the statistical analysis.

For each study group, the number of patients with at least one of the following will be described:

- One AE related to the oral targeted therapy.

- One AE related to the oral targeted therapy of grade  $\geq 3$ .
- One SAE related to the oral targeted therapy.
- One AE related to the oral targeted therapy leading to a definitive discontinuation of the drug.
- One AE related to the oral targeted therapy leading to a temporary discontinuation of the drug.
- One AE related to the oral targeted therapy leading to a dose reduction.

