### **5.3 SAFETY DATA TOLERANCE**

#### **5.3.1 Safety endpoints**

The current study will collect the AEs as follows:

- Number of adverse events (AE) related to the oral targeted therapy.
- Number of AE related to the oral targeted therapy of grade  $\geq 3$ .
- Number of serious adverse events (SAE) related to the oral targeted therapy.
- Number of AE related to the oral targeted therapy and leading to a definitive or temporary discontinuation of the drug, or to a dose reduction.

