### 5.3.2.1      Definition of adverse events

#### **Adverse event**

An AE is defined as any untoward medical occurrence, including an exacerbation of a pre-existing condition, in a person taking part in a clinical study. The event does not necessarily have to have a causal relationship with the study.

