#### **Causal relationship of adverse events with the targeted oral therapy**

Medical judgment should be used to determine the relationship with the oral targeted therapy while considering all relevant factors, including pattern of reaction, temporal relationship, de-challenge or re-challenge, confounding factors such as concomitant medication, concomitant diseases and relevant history.

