### 5.3.2.2 Adverse event and reporting

All SAEs, non-serious AEs and others PV information, occurring during the course of the study (i.e., from signing the informed consent onwards through D90) will be collected, documented and reported to the sponsor or the CRO in charge of the data monitoring by the investigator on the appropriate reporting forms (AE page of the CRF or SAE form).

For each adverse event, the investigator will provide the onset date, end date, intensity, treatment required, outcome, seriousness, causal relationship, and action taken with the targeted oral therapy. The investigator will determine the relationship of the oral targeted therapy to all AEs.

All personnel involved in the study (investigator, the Patientys call centre nurse, general practitioner, centre personnel...) must immediately report any SAE that they encounter to the CRO responsible of the data monitoring. The event must be notified within 24h, via telephone or FAX using the SAE reporting form to:

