## 7. STATISTICAL METHODS AND DETERMINATION OF PATIENTS SAMPLE SIZE

### 7.1 STATISTICAL DESIGN

This is a routine clinical practice, randomised, open-label, multicentre, study.

Patients will be randomised in one of the following 2 groups:

- Group ‘without remote additional personalised nurse-led follow-up’: patients will receive the healthcare given routinely by the medical team (100 patients).
- Group with ‘remote additional personalised nurse-led follow-up’: patients will receive telephone calls from a nurse in addition to the healthcare given routinely by their medical team (300 patients).

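### The safety analysis keeps only AEs that open-label investigators judge drug-related, so the arm contrast depends on attribution and unrelated SAEs, including deaths, are not tabulated by arm

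*Combined protocol and SAP*

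**What the plan says.** Collection is all-cause. Section 5.3.2.1 defines an AE so that "The event does not necessarily have to have a causal relationship with the study". Section 5.3.2.2 extends collection, from consent to D90, to "All SAEs, non-serious AEs and others PV information, occurring during the course of the study", and requires SAEs to be notified whether or not a causal link is suspected.

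Analysis is not all-cause. Section 7.3.4 states: "Only events considered related to oral targeted therapy will be considered in the statistical analysis". All six categories that it lists are limited to related events, as are the safety endpoints in the synopsis and Section 5.3.1, for example "Number of serious adverse events (SAE) related to the oral targeted therapy".

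On who decides, Section 5.3.2.2 says "The investigator will determine the relationship of the oral targeted therapy to all AEs", and Section 5.3.2.1 gives the basis: "Medical judgment should be used to determine the relationship with the oral targeted therapy while considering all relevant factors". Section 7.1 describes the design: "This is a routine clinical practice, randomised, open-label, multicentre, study". In the nurse arm, Sections 5.3.2 and 6.2.3 have the nurse send a same-day call report with AE pages, to which the investigator adds intensity and causality.

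On the type of analysis, Section 7.3.4 says: "For each study group, the number of patients with at least one of the following will be described". It names no test.

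**The concern.** Both arms take the same drug. What is randomised is the telephone follow-up, and safety is a stated secondary objective. Relatedness to the drug is a reasonable way to look at toxicity, but here it is the only way, and it depends on a judgement made with knowledge of the arm. The process behind that judgement also differs by arm: one arm has a nurse who prompts for listed events and supplies AE pages, and the other has no such route.

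Two things are at stake. A difference between arms in related AEs, or the absence of one, could come partly from attribution. And in stage IIIb/IV lung cancer, a death or hospitalisation judged unrelated to the drug meets the SAE definition yet enters no planned safety summary by arm.

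**Working it through.** The plan states no figure on this point, so there is none to reproduce. The check is a comparison of sections, followed by an illustration of size.

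**Comparison of sections**

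1. Collected: all AEs and SAEs, any cause, consent to D90 (Sections 5.3.2.1, 5.3.2.2).
2. Analysed: related events only (Section 7.3.4, with endpoints to match in Section 5.3.1 and the synopsis).
3. The filter between 1 and 2: the investigator's medical judgement. The investigator's team also sends the randomisation fax (Section 3.1), so the arm is known. No blinded or independent causality review is described, and Section 8.7 records that no independent surveillance committee was set up.
4. Difference by arm: eight nurse calls in one arm only (Section 3.1), with a list of events to collect (Section 6.2.3) and AE pages passed on for causality rating (Sections 5.3.2, 6.2.3).
5. Other by-arm information: emergency admissions and unplanned hospitalisations are limited to treatment-related ones in Section 5.2.1, although Section 7.3.3 omits that qualifier. Time to first dose modification or interruption (Section 7.3.2) and dose not taken (Section 7.3.3) do not depend on AE attribution, but they do not show SAEs or deaths.
6. Completeness: Section 3.1 has the nurse collect AEs related to treatment, Section 6.2.3 has her collect AEs met while taking treatment, and Section 5.3.2.2 requires all AEs. These do not agree.

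**Illustration of size (assumed attribution rates)**

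Related risk = all-cause risk × probability of being judged related. Take the same all-cause risk in both arms, one event per affected patient, and 60% judged related in the control arm.

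| All-cause risk, both arms | Control, 60% related | Nurse arm, 70% related | Nurse arm, 80% related |
|---|---|---|---|
| 20% | 12% | 14% | 16% |
| 30% | 18% | 21% | 24% |
| 50% | 30% | 35% | 40% |

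The ratio is 0.70/0.60 = 1.17 or 0.80/0.60 = 1.33 at every risk, while the true ratio is 1.00. If the assumed gap ran the other way, it would be 0.60/0.70 = 0.86.

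These ratios suit event counts, as in Section 5.3.1, or categories with about one event per patient, such as SAEs. Section 7.3.4 counts patients with at least one related event. If each affected patient has k AEs judged independently (also an assumption), the ratio is (1 − 0.3^k)/(1 − 0.4^k):

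- k = 1: 0.70/0.60 = 1.17
- k = 2: 0.91/0.84 = 1.08
- k = 3: 0.973/0.936 = 1.04
- k = 5: 0.998/0.990 = 1.01

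The row for any related AE is therefore much less sensitive to attribution than 1.17 suggests when patients have several AEs.

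**The case against.** The related-only restriction is a consistent endpoint definition, not a slip: the synopsis, Section 5.3.1 and Section 7.3.4 agree. The calls are meant to help manage drug-related AEs, so related toxicity is a natural measure. Section 5.3.2.1 also records clinically relevant worsening of the underlying disease as an AE, so all-cause rows would mix in progression. This supports keeping the related-only rows. It does not support having them alone, because the randomised contrast is the follow-up and not the drug.

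All-cause rows are not free of bias either. The same unblinded investigator assigns intensity, so a grade 3 or higher row is still an arm-aware judgement. Eight extra prompted contacts in one arm can raise the any-AE row without any real difference. Both points stand and limit what the fix can achieve.

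A reader might infer several stronger things that the documents do not support:

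- That the safety comparison is shown to be biased by some amount or in some direction. No attribution rate is given, and the 60%, 70% and 80% are assumptions.
- That the nurse decides causality, or that her report is a list of expected drug reactions. The investigator rates causality in both arms, and Section 6.2.3 gives events to collect in particular, with an open category at the end.
- That all-cause SAEs will never be reported by arm. These documents plan no such table, but Sections 7.4 and 8.3.1 refer to an SAP still to be finalised before database lock.

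**Conclusion.** The point holds in a limited form. A stated rule removes collected safety data through a judgement made with knowledge of the arm and on inputs that differ by arm, and no all-cause summary is planned against which to check the result. The consequence is for reading a descriptive secondary table. It would be tempting to call this an inflated error rate, but Section 7.3.4 names no test, and neither type I error nor the primary comparison of cumulated dose is touched.

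The size cannot be estimated from the documents. The ratio of 1.17 rests on equal all-cause risk and assumed attribution of 70% against 60%. It applies to event counts or single-event categories, and falls to 1.08 and 1.04 for patients with two and three independently judged AEs. The absence of unrelated SAEs and deaths from the planned safety summaries needs no assumption: it follows directly from the text.

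**What to change.** Add by-arm rows to Section 7.3.4, whatever the cause: chiefly SAEs (including deaths), plus grade 3 or higher AEs and any AE. Keep the related-only rows beside them.

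Reconcile Sections 3.1 and 6.2.3 with Section 5.3.2.2 on whether the nurse collects all AEs or only those related to treatment. Otherwise the all-cause rows may be incomplete in one arm.

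State with the table that all-cause rows remove dependence on attribution but not unequal ascertainment from the eight extra calls, nor unblinded grading. The all-cause SAE row is then the most informative, and the any-AE row must be read with caution.

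The cost is a few table rows and a short clarification. Section 5.3.2.2 already requires the data, so no new patients, visits or CRF fields are needed, and the rows can go into the SAP before database lock. Patient contacts made before the sections are reconciled may still have been recorded under the narrower reading, and the report should say so.
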